	
▪ Grade ≥ 3 nausea, vomiting or diarrhea that resolves to grade ≤ 2 within 72 hours, with maximal medical intervention▪ Grade 3 fatigue, asthenia, anorexia, fever or constipation that resolves to grade ≤ 2 within 14 days▪ Grade ≥ 3 asymptomatic changes in alkaline phosphatase, hypomagnesemia, hyperglycemia or hypophosphatemia▪ Grade 3 increases in transaminases confirmed upon repeat testing lasting ≤ 5 days▪ Any Grade ≥ 3 electrolyte abnormality that is corrected to Grade ≤ 2 within 24 hours▪ Non-hematologic laboratory Grade 3 AE that is asymptomatic and/or rapidly reversible (returned to baseline or to Grade ≤ 1 within 7 days) unless identified as clinically relevant by the Investigator; and (in non-diabetic patients) singular or non-fasting elevations in blood glucose 
• Any case of Hy's law defined as AST or ALT $>3 \times$ ULN with concurrent total bilirubin $>2 \times$ ULN, absence of cholestasis (elevated ALP $>2 \times$ ULN), and no alternative etiology, which can explain the combination of increased AST or ALT and total bilirubin, such as viral hepatitis A through E, other preexisting or acute liver disease, liver acute GVHD, or another drug capable of causing the observed injury• Any dose reduction required during Cycle 1 due to grade ≥ 3 adverse events• Any treatment delay of >7 consecutive days during Cycle 1 due to study drug-related Grade ≥ 3 adverse events that fails to resolve to baseline or grade ≤ 1• Any Grade ≥ 3 gastrointestinal, genitourinary or central nervous system hemorrhage• Any grade 4 or 5 nonhematological adverse reaction• Any death unless unequivocally due to underlying disease (or extraneous cause) 
Any adverse reaction unrelated to active GVHD that leads to the study drug PLX51107 dose reduction or withdrawal should be considered a DLT.
 
Grade 3 or higher adverse events occurring past 28-days must be recorded and reviewed for final analysis and for Phase 2 dose evaluation.

Eligibility	Patients with a diagnosis of treatment-refractory acute GVHD are eligible. Patients must be refractory to first-line steroid therapy and failed one or more salvage therapy regimens. Patients with a contraindication to the use of steroids are not deemed steroid-refractory and are ineligible. Patients

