 - New onset non-hematological clinical and laboratory toxicity grade ≥ 3 lasting >72 hours with the exception of the following events:
 - Grade ≥ 3 nausea, vomiting or diarrhea that resolves to grade ≤ 2 within 72 hours, with maximal medical intervention
 - Grade 3 fatigue, asthenia, anorexia, fever or constipation that resolves to grade ≤ 2 within 14 days
 - Grade ≥ 3 asymptomatic changes in alkaline phosphatase, hypomagnesemia, hyperglycemia or hypophosphatemia
 - Grade 3 increases in transaminases confirmed upon repeat testing lasting ≤ 5 days
 - Any Grade ≥ 3 electrolyte abnormality that is corrected to Grade ≤ 2 within 24 hours
 - Non-hematologic laboratory Grade 3 AE that is asymptomatic and/or rapidly reversible (returned to baseline or to Grade ≤ 1 within 7 days) unless identified as clinically relevant by the Investigator; and (in non-diabetic patients) singular or non-fasting elevations in blood glucose
 - Any case of Hy's law defined as AST or ALT $>3 \times$ ULN with concurrent total bilirubin $>2 \times$ ULN, absence of cholestasis (elevated ALP $>2 \times$ ULN), and no alternative etiology, which can explain the combination of increased AST or ALT and total bilirubin, such as viral hepatitis A through E, other preexisting or acute liver disease, liver acute GVHD, or another drug capable of causing the observed injury
 - Any dose reduction required during Cycle 1 due to grade ≥ 3 adverse events
 - Any treatment delay of >7 consecutive days during Cycle 1 due to study drug-related Grade ≥ 3 adverse events that fails to resolve to baseline or grade ≤ 1
 - Any Grade ≥ 3 gastrointestinal, genitourinary or central nervous system hemorrhage
 - Any grade 4 or 5 nonhematological adverse reaction
 - Any death unless unequivocally due to underlying disease (or extraneous cause)

Any adverse reaction unrelated to active GVHD that leads to the study drug PLX51107 dose reduction or withdrawal should be considered a DLT.

Grade 3 or higher adverse events occurring past 28-days must be recorded and reviewed for final analysis and for Phase 2 dose evaluation.

Hold Parameters

		Occurrence	Resume	Dose
Neutropenia	Grade 4 (ANC <500/mm3)	1st	Upon improvement to Grade ≤2 (ANC >1000/mm3). GCSF support may be used.	If improved within 7 days, continue same dose. If no improvement within 7 days, permanently discontinue drug.

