		2nd	Upon improvement to Grade ≤2. GCSF support may be used.	If improved within 7 days, dose reduce by one level. If no improvement within 7 days, permanently discontinue drug.
		3rd	Permanently discontinue study drug.	
Thrombocytopenia	Grade 4 (platelet count <25,000/mm3)	1st	Upon improvement to Grade ≤2 (platelet count >50,000/mm3) within 14 days	If improved within 14 days, continue same dose. If no improvement within 7 days, permanently discontinue drug.
		2nd	Upon improvement to Grade ≤2 (platelet count >50,000/mm3) within 14 days	If improved within 14 days, dose reduce by one level. If no improvement within 7 days, permanently discontinue drug.
		3rd	Permanently discontinue study drug.	
Other non-hematologic	Grade 3 adverse events	1st	Hold until improved to Grade ≤1	If improved within 5 days, continue same dose. If >5 days, dose reduce by one level.
		2nd	Hold until improved to Grade ≤1.	If improved within 5 days, dose reduce by one

				level. If >5 days, permanently discontinue.
Other non-hematologic	Grade 4 adverse events	1st	Permanently discontinue study drug	

Treatment Plan

Investigational product

PLX51107 will be supplied by Plexxikon in 20 mg tablet formulations. Each participating site must have sufficient supply for one cycle (28 days) available prior to enrollment of each patient. Additional months' supplies will be ordered by the site accordingly.

All patients will receive prednisone 1-2 mg/kg orally daily (may be divided into 2 doses) or MP IV equivalent. Corticosteroids may be tapered per institutional guidelines but initiated no sooner than 7 days after Study Day 1 and to no less than prednisone 0.25mg/kg daily before Study Day 28. The minimum dose of prednisone at Study Day 1 is 1mg/kg (or MP IV equivalent).

Treatment Dosage and Administration

The first day of administration is deemed Study Day 1. The dosage administered is determined by dose level in Table 1 and in observance of DLT or SAE considerations.

Treatment will be administered orally daily. The first day of administration is Study Day 1. PLX51107 should be taken at approximately the same time of day. On Study Days 1, 8, and 15 when PK/PD sample collections are drawn, patients should fast 8 hours prior and 1 hour after daily dose administration. On other days when, there are no scheduled PK/PD sample collections, patients should fast 2 hours prior and 1 hour after daily dose administration.

Dosing Delays or Missed Doses

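### Both Grade 4 platelet hold rows give opposite instructions to a patient who recovers late, and at first occurrence in Cycle 1 the DLT count can turn on which one is followed

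*Combined protocol and SAP*

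**What the plan says.** All references are to the combined protocol and SAP.

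- **Hold Parameters, Thrombocytopenia, 1st occurrence, Dose column:** "If improved within 14 days, continue same dose. If no improvement within 7 days, permanently discontinue drug".
- **Same table, 2nd occurrence, Dose column:** "If improved within 14 days, dose reduce by one level. If no improvement within 7 days, permanently discontinue drug".
- **Same table, Resume column, both rows:** "Upon improvement to Grade ≤2 (platelet count >50,000/mm3) within 14 days".
- **Hold Parameters, Neutropenia:** 7 days stands in both sentences of each row. First occurrence: "If improved within 7 days, continue same dose. If no improvement within 7 days, permanently discontinue drug". Second occurrence: "If improved within 7 days, dose reduce by one level. If no improvement within 7 days, permanently discontinue drug".
- **Dose limiting toxicity (DLT), hematological list:** the platelet criterion is Grade 4 thrombocytopenia that persists beyond 14 days.
- **DLT section, closing sentence on withdrawal:** an adverse reaction not related to active GVHD that leads to a dose reduction or to withdrawal of PLX51107 counts as a DLT.
- **DLT section, treatment-delay item:** "Any treatment delay of >7 consecutive days during Cycle 1 due to study drug-related Grade ≥ 3 adverse events", with the condition "adverse events that fails to resolve to baseline or grade ≤ 1". The Synopsis carries the same item.
- **Study Design:** a level can be the biologically effective and tolerable dose (BETD) only with 0 or 1 DLT among six patients, alongside biological activity in at least five. The Synopsis stops accrual and de-escalates at 2 or more DLTs in six.

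**The concern.** The two sentences in each platelet Dose cell are meant to divide patients into those who go on and those who stop, but their time limits overlap. A patient whose platelets recover after day 7 and by day 14 can fall under both. One site could keep that patient on drug while another, reading the same cell, removes the patient for good. The registration section provides for subsites, so different teams may apply the table.

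Two things are at stake. The first is the patient's treatment: either an early permanent stop in a population described as having no other options, or continued dosing where the table also says to stop. The second is the primary endpoint. Withdrawal for a drug-related reaction is itself a DLT, so the choice of sentence can add a DLT to a cohort of six in which the second DLT ends accrual at that level.

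**Working it through.** The plan states no figure on this point, so the check sets the rules side by side. Days are counted from the start of the hold. The table does not name a starting point, but both sentences share whichever clock is used, so the conflict does not depend on it.

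**Step 1. Which instruction applies, taking improvement as Grade 2 or better (the only level that the Resume column names).**

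| Day Grade 2 or better is reached | 1st occurrence | 2nd occurrence |
|---|---|---|
| 7 or earlier | same dose | reduce one level |
| 8 to 14 | same dose **and** discontinue | reduce one level **and** discontinue |
| 15 or later | discontinue | discontinue |

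The overlap is 14 − 7 = 7 days, in 2 of the 2 platelet rows that carry a time limit.

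**Step 2. The narrower reading.** Suppose that a move from Grade 4 to Grade 3 by day 7 already counts as improvement. The stop sentence then does not apply to that patient, and only the 14-day limit governs. A patient still at Grade 4 on day 7 who reaches Grade 2 or better by day 14 still meets both sentences. The conflict shrinks but does not vanish.

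**Step 3. Which number looks out of place.** Each platelet row says 14 days twice (Resume column and first Dose sentence) and 7 days once. The platelet DLT criterion is also set at 14 days. The neutropenia rows use 7 throughout, matching the neutropenia DLT limit of more than 7 days. The 7 in the platelet stop sentence is therefore probably carried over from the neutropenia rows. That is an inference; the documents do not say so.

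**Step 4. DLT status for a drug-related event in Cycle 1 that falls in the overlap.**

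- *1st occurrence, discontinue:* a DLT through the withdrawal sentence.
- *1st occurrence, same dose:* the platelet criterion is not met, because Grade 4 did not last beyond 14 days. Only the delay item could make it a DLT.
- *2nd occurrence, either course:* a dose reduction and a withdrawal are both DLTs under the closing sentence. Only dosing is in conflict; the count is not.

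**Step 5. The delay item at 1st occurrence, for a hold longer than 7 days on the same-dose course.**

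- If the item does not cover platelets: not a DLT, so the two courses differ.
- If it covers platelets and resolution is judged when dosing resumes: a DLT only if the count is then neither at baseline nor at Grade 1 or better. Resumption needs more than 50,000/mm³, and the entry floor is 50 × 10⁹/L, which is the same level. A patient who entered near the floor can be back at baseline on resuming, so the courses differ. One who entered much higher may not be, and then both courses are DLTs.
- If it covers platelets and resolution is judged at day 7: a patient who is not yet above 50,000/mm³ has not resolved, so both courses are DLTs.

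**Step 6. Effect on the dose decision.** One patient classified differently can take a level from 1 of 6 DLTs (eligible as BETD) to 2 of 6 (accrual stops and the dose goes down).

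**The case against.** The strongest reply on dosing is that the cell describes a two-step rule: look for some rise by day 7, then allow until day 14 for full recovery. In ordinary usage a rise from Grade 4 to Grade 3 is an improvement. This part stands: the documents do not establish that every recovery on days 8 to 14 is caught. A reader might infer the full seven-day window as a certainty, but it holds only if improvement means Grade 2 or better in the stop sentence as well. The reply does not remove the conflict, because the table states no sequence, and the patient still at Grade 4 on day 7 who recovers by day 14 is covered by both sentences as written.

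The strongest reply on the DLT count is that the delay item may make both courses DLTs. It is listed after the non-hematological heading, but its wording is general, and a neighbouring item limits itself expressly to nonhematological reactions, which would be unnecessary if the whole list were so limited. Bullet levels in the available text are not reliable enough to decide. This also stands in part. A reader might infer that the two courses always give different DLT counts; the documents support only that they can. Nor would a tally of the rule combinations in which the courses differ measure the size of the problem. It would count interpretations rather than patients, and it changes with the time at which resolution is judged, which the item does not state.

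Finally, the event may be uncommon, and a changed BETD decision also needs a cohort at the boundary between one and two DLTs. That is fair. The documents give no rate, so neither a high nor a low frequency can be claimed.

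**Conclusion.** The dosing conflict is real and stands in both platelet rows; nothing elsewhere in the documents reconciles the two limits. At a minimum it affects a patient still at Grade 4 on day 7 who reaches Grade 2 or better by day 14. If improvement has the meaning that the Resume column gives it, it affects every recovery on days 8 to 14.

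The effect on the DLT count is conditional. It needs a first occurrence in Cycle 1, at least possibly related to PLX51107, with recovery inside the overlap, and a delay item that either does not reach platelets or is satisfied because the count has returned to baseline or to Grade 1 or better. At second occurrence in Cycle 1 the count is the same on either course. The point should be fixed as a short correction to a safety rule; it does not show that the dose-finding design fails.

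**What to change.** In the stop sentence of both platelet rows, change 7 days to 14 days. Each recovery day then has one instruction: by day 14, same dose (1st occurrence) or one level lower (2nd); after day 14, discontinue. This agrees with the Resume column and with the platelet DLT criterion.

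Add one sentence, in the Synopsis and in the DLT section, saying whether the item beginning "Any treatment delay of >7 consecutive days during Cycle 1 due to study drug-related" applies to platelet holds and, if it does, when resolution is judged.

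Aligning everything at 7 days would also remove the conflict. It needs the Resume entry and the first Dose sentence changed in both rows (2 × 2 = 4 numbers). It would also leave the platelet DLT criterion largely redundant, because a related Cycle 1 event not recovered by day 7 would already be a DLT through withdrawal. If the clinical team does want a day-7 check for some early rise, the table should say so and define the rise required.

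The cost of the preferred option is one number in each of two cells and one sentence stated in two places. It adds no patients, visits or procedures.

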No Response (NR) is defined as no improvement and/or progression of acute GVHD symptoms in any organ.

Number of Subjects

The minimum number of patients accrued to the Phase 1 portion is 6 patients (3 patients with ≥ 2 DLTs at Dose Levels 1 and 0) with maximum of 18 patients (6 patients each at Dose Levels 1-3).

Duration

We anticipate a screen failure rate of approximately 40% and enrolling a maximum 18 patients. The expected time to screen 45 patients at our center would span approximately 2 years. Patients will require at least 6 months of follow-up (6 months after initiation of study drug or 30 days after discontinuation of study drug). Total duration of this trial is expected to take approximately 2.5 years.

Study Calendar

	Cycle 1				Cycle 2				†Cycle 3+	SAE/DLT	*6-mo F/U	EOT	
	Screening	Day 1	Day 8	Day 15	Day 22 ±3	Day 1	Day 8 ±3	Day 15 ±3	Day 22 ±3	Day 1 ±3	±3 days	±7 days	±7 days
Informed Consent/Eligibility Review	X												
Concomitant Medication Review	X		X	X	X	X	X	X	X	X	X	X	X
Physical Exam with Vital Signs	X		X	X	X	X	X	X	X	X	X	X	X
ECOG Performance Status	X		X	X	X	X	X	X	X	X	X	X	X
PLX51107		Daily											
Adverse Event Evaluations		X	X	X	X	X	X	X	X	X	X	X	X
Complete Blood Count (CBC)	X		X	X	X	X	X	X	X	X	X	X	X
Comprehensive Metabolic Panel (CMP)	X		X	X	X	X	X	X	X	X	X	X	X
PT/aPTT/INR	X		X	X	X	X	X	X	X	X	X	X	X
Serum Pregnancy Test	X												
GVHD Staging	X		X	X	X	X	X	X	X	X	X	X	X
Relapse, Survival			X	X	X	X	X	X	X	X	X	X	X
Peripheral Blood for PK		X	X	X									
Peripheral Blood for PD		X	X								X		
†Peripheral Blood for MAP		X	X	X	X	X							
Peripheral Blood for Immune Reconstitution		X	X	X	X	X				X	X	X	X

†Applies to C3D1, C4D1, C5D1, and C6D1

*6 month follow-up may overlap with EOT. In this case, these will be deemed EOT days.

‡MAP refers to MAGIC Algorithm Probability

Please note: $C_n D_{28} = C(n+1)D_1$

Dose limiting toxicity (DLT)

DLTs are defined as AEs or laboratory abnormalities occurring during the first cycle (28 days) of study drug administration that are at least possibly related to PLX51107, deemed to be clearly unrelated to disease progression, concurrent illness or concomitant medication and that meet one of the following NCI CTCAE v5.0 criteria below.

- **Hematological toxicities**
 - Grade >3 neutropenia lasting >7 days
 - Grade ≥ 3 febrile neutropenia
 - Grade 4 thrombocytopenia lasting >14 days despite study drug discontinuation
- **Non-hematological toxicities**

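### The hold table resumes PLX51107 at the same dose after a first Grade 3 GI, GU or CNS hemorrhage that recovers within 5 days, although a drug-related bleed of that grade is a DLT

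*Combined protocol and SAP*

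**What the plan says.** Two parts of the section on dose limiting toxicity bear on this point.

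**DLT definition.** A DLT must occur in the first 28-day cycle, be at least possibly related to PLX51107, and be "deemed to be clearly unrelated to disease progression, concurrent illness or concomitant medication". Among the criteria that then apply are:

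- "Any Grade ≥ 3 gastrointestinal, genitourinary or central nervous system hemorrhage", with no minimum duration;
- "New onset non-hematological clinical and laboratory toxicity grade ≥ 3 lasting >72 hours", subject to a list of exempt events;
- febrile neutropenia of Grade 3 or higher, also with no minimum duration;
- any Hy's law case;
- "Any dose reduction required during Cycle 1 due to grade ≥ 3 adverse events".

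A closing sentence adds that an adverse reaction unrelated to active GVHD that "leads to the study drug PLX51107 dose reduction or withdrawal should be considered a DLT".

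**Hold Parameters table.** For a first Grade 3 event in the other non-hematologic row the instruction is "Hold until improved to Grade ≤1", followed by "If improved within 5 days, continue same dose" or, with slower recovery, "If >5 days, dose reduce by one level". A second such event brings a one-level reduction even when recovery is within 5 days. Grade 4 non-hematologic events lead to permanent discontinuation. In the neutropenia row, a first Grade 4 episode (ANC below 500/mm3) that improves to Grade 2 or lower within 7 days also continues at the same dose. No cell refers to whether the event was a DLT.

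**The concern.** The link between dosing and DLTs runs one way. A reduction or withdrawal can make an event a DLT, but nothing in the visible text makes a DLT lead to a reduction or withdrawal. The resumption dose depends on grade, speed of recovery and number of occurrences.

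For hemorrhage this matters to the individual patient. A bleed that counts as a DLT has already been judged possibly drug-related and clearly not explained by disease progression, concurrent illness or other drugs. If the table is followed as written, that patient receives the full dose again. The section on concomitant medications acknowledges that exposure-toxicity information for PLX51107 is not yet available, and the inclusion criteria admit patients with platelets as low as 50 x 10^9/L. Because other wording lets an investigator reduce or stop, two patients with the same bleed could also be handled differently.

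**Working it through.** The plan gives no figure to reproduce. The check sets each DLT criterion beside the hold row that governs it.

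**1. Grade 3 GI, GU or CNS hemorrhage.** The DLT section lists it under non-hematological toxicities, so the only row that fits is other non-hematologic, Grade 3. Because the DLT line has no minimum duration, every first bleed of this kind that reaches Grade 1 or lower within 5 days is both a DLT (if it passes the attribution test in Cycle 1) and resumed at the same dose. If recovery takes longer than 5 days, the table already reduces. At Grade 4 it discontinues.

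**2. Febrile neutropenia.** With ANC below 500/mm3 the patient falls in the Grade 4 neutropenia row. A first episode that recovers within 7 days continues at the same dose, although febrile neutropenia is a DLT at any duration. With ANC of 500/mm3 or more there is no row of its own.

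**3. Non-exempt Grade 3 event lasting more than 72 hours.** The two clocks measure different things: the DLT clock is time at Grade 3 or above, and the hold clock is time to Grade 1 or lower. Let T be hours at Grade 3 and g be hours then spent at Grade 2.

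- DLT: T > 72.
- Same dose, if both clocks start at onset: T + g ≤ 5 x 24 = 120.
- Overlap: 72 < T ≤ 120 − g, a width of 48 − g hours.

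So 48 hours is the maximum, reached only if the event drops straight from Grade 3 to Grade 1 or lower. With g = 24, for example, 24 hours remain. The table does not say when its 5 days start. If they run from a hold that begins h hours after onset (an assumption), the width is 48 + h − g: at most 72 hours for h = 24 and 96 hours for h = 48. Many events are outside this overlap because they are exempt, such as fatigue resolving to Grade 2 or lower within 14 days or transaminase rises of 5 days or less. Nausea, vomiting or diarrhea that has not fallen to Grade 2 or lower by 72 hours is not exempt.

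**4. Hy's law.** It has no row. Where a case would land depends on CTCAE grade limits that the documents do not give. A case with a Grade 3 component that recovered within 5 days would meet the same cell as the hemorrhage.

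**5. Where the table and the DLT list agree.** Grade 4 neutropenia without improvement within 7 days is discontinued. Grade 4 thrombocytopenia lasting more than 14 days is discontinued. Grade 4 non-hematologic events are discontinued.

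**6. Size of the dose difference.** From Table 1, same dose over one level lower: 40/20 = 2.0; 80/40 = 2.0; 120/80 = 1.5. The 20 mg level has nothing below it.

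**The case against.** The strongest case for the plan is that DLTs govern cohort decisions while hold rules manage individuals, and nothing requires the two to match. The table is graduated: it waits for recovery, reduces when recovery is slow or the event recurs, and stops at Grade 4. One rechallenge at the same dose can be defended in patients whom the background section describes as having no other therapeutic options. There is also room for judgment. Dosing is daily as tolerated (Study Design), it takes DLTs and SAEs into account (Treatment Dosage and Administration), toxicity is listed as a reason to end dosing (Duration of Therapy), and the calendar has an SAE/DLT visit.

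Much of this stands. For the 72-hour to 5-day events and for febrile neutropenia, same-dose resumption is a trade-off that the sponsor may reasonably choose. It does not settle hemorrhage. The general wording permits an override of an explicit cell but does not require one.

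A second limit is that the text under the heading Withdrawal was not available to this review, and a rule on what follows a DLT could sit there. If it does, the table still has to be reconciled with it.

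A reader might infer more than the documents support:

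- *That the table breaks a rule to stop or reduce after a DLT.* No visible text states such a rule.
- *That dose escalation is compromised.* The event counts as a DLT whatever dose follows, so the 3+3 decisions stand.
- *That GVHD diarrhea is caught up in this.* Diarrhea attributed to GVHD fails the attribution test and is not a DLT.

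**Conclusion.** The point holds as a patient-safety weakness in the hold table, and it is firmest for Grade 3 GI, GU or CNS hemorrhage, where the same-dose instruction covers every first bleed that recovers within 5 days. It also holds for a first febrile neutropenia with ANC below 500/mm3 that recovers within 7 days, and, within a window of at most 48 hours if both clocks start at onset, for non-exempt Grade 3 events. For those two it is a matter to clarify rather than a defect.

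The consequence is a daily dose 1.5 to 2 times the next level down. The documents give no event rates, so the number of patients affected cannot be estimated. The conclusion rests on the visible text and assumes that the table is followed as written.

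**What to change.** Add to the Hold Parameters table:

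*After a Grade 3 GI, GU or CNS hemorrhage at least possibly related to PLX51107, in any cycle, and after any Hy's law case, PLX51107 is not resumed at the same dose. It is permanently discontinued or, after recovery, resumed one level lower (120 to 80, 80 to 40, 40 to 20 mg; discontinue if at 20 mg). When the event is a DLT, a resulting Cycle 1 reduction is part of that DLT and is not counted again.*

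The rule covers all cycles because dosing can run to 7 months and the bleeding risk does not end at Day 28. The count-once sentence is needed because a Cycle 1 reduction is itself a listed DLT, and the BETD rule allows 0-1 DLTs while the stopping rule counts patients. Without it, one patient could be read as two DLTs.

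Optionally, state whether same-dose resumption is intended after febrile neutropenia and after non-exempt Grade 3 events of more than 72 hours that recover by day 5. If the Withdrawal text already holds a post-DLT rule, reconcile the table with it.

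The cost is a short paragraph, with no extra patients, visits or tests. Biological activity is read from Day 1 exposure, so a later reduction does not change it. There are two downsides. A few recovered patients lose same-dose rechallenge. And a Cycle 1 bleed that is possibly related but fails the rest of the attribution test would now be reduced or stopped, which the closing DLT sentence could turn into a DLT if the bleed is unrelated to active GVHD. The sponsor should say how such a case is counted.
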